6. STUDY TREATMENT

6.1 Description of Study Drug and Supplies

The MGA271 drug product is a sterile, preservative-free, clear to slightly opalescent, colorless to pale yellow or pale brown solution supplied at a protein concentration of 25 mg/mL in a single-use 20 mL vial containing 17 mL (425 mg) MGA271. The product is formulated in 0.95 mg/mL sodium acetate trihydrate, 0.18 mg/mL glacial acetic acid, 90 mg/mL sucrose, 0.1 mg/mL polysorbate 80 and Water for Injection, United States Pharmacopeia (USP) at a pH of 5.1.

MGA271 is supplied as a sterile aqueous solution packaged in a USP and Ph. Eur. conforming Type I borosilicate, 20 mL clear glass vial with a 20 mm FluroTec-coated 4432/50 gray butyl rubber serum stopper. The vial is sealed with a 20 mm TruEdge aluminum closure with a plastic overseal. MGA271 will be administered by IV infusion over 120 minutes. A sterile, non-pyrogenic, low-protein binding polyethersulfone (PES) 0.2 micron in-line filter administration set must be used for IV administration of MGA271. MGA271 must not be administered as an IV push or bolus.

Under no circumstances is the Investigator allowed to release these clinical supplies for use by another physician not named on Form FDA 1572 or to administer study drug to a patient who is not enrolled in this study. Study drug must be dispensed at an institution specified on Form FDA 1572.

Requests to MacroGenics, Inc for additional study drug should be made at least 2 weeks in advance.

6.2 Drug Preparation

6.2.1 General Guidelines and Precautions

The calculated dose will be administered based on the patient's actual weight at Day 1. Significant (\geq 10%) change in body weight from baseline should prompt recalculation of dose.

Infusion or allergic reactions may occur with the infusion of monoclonal antibodies and other protein-based therapeutics. Precautions for anaphylaxis should be observed during MGA271 administration. Supportive measures may include, but are not limited to: epinephrine, antihistamines, corticosteroids, IV fluids, vasopressors, oxygen, bronchodilators, diphenhydramine, and acetaminophen. Please refer to **Section 6.4.4** for specific guidelines regarding the management of infusion reactions. Supportive care measures consistent with optimal patient care will be provided throughout the study according to institutional standards.

6.2.2 MGA271

- Inspect parenteral drug products visually for particulate matter and discoloration prior to administration. Discard vial if solution is cloudy, there is pronounced discoloration (solution may have pale-yellow color), or there is foreign particulate matter.
- The desired amount of MGA271 should be withdrawn from the vial(s) and diluted to the appropriate final concentration with 0.9% Sodium Chloride Injection USP, according to the instructions provided in the Pharmacy Manual.
- The infusion bag containing MGA271 should be gently inverted to mix the solution. THE BAG MUST NOT BE SHAKEN; excessive agitation may cause aggregate formation.
- Discard partially used vials of MGA271
- Administration of study drug should begin immediately after preparation but no later than 6 hours after preparation (see Pharmacy Manual). If there is a delay in administration of study drug such that it will not be administered on the day of preparation, the Medical Monitor should be notified immediately. Instructions on how to proceed will be provided.

IRB#: IRB0010377

6.2.3 Placebo or Control

There will be neither placebo nor active control drug for this study.

6.3 Study Drug Administration

- Do not mix MGA271 with, or administer as an infusion with, other medicinal products.
- Administer the diluted solution over 120 minutes through an intravenous line using an infusion pump. A sterile, non-pyrogenic, low-protein binding polyethersulfone (PES) 0.2 micron in-line filter administration set must be used for IV administration of MGA271.
- Do not use non-polyolefin IV infusion bags.

6.4 Potential Adverse Events and Supportive Care Measures

6.4.1 Infusion Related Reactions Including Cytokine Release Syndrome

MGA271 is an immune modulating agent that may lead to T-cell activation and killing of the tumor cell. Activation of T cells is associated with the production of various cytokines.

Infusion reactions (including cytokine release syndrome [CRS]) associated with MGA271 administration should be managed according to the standard practice of medicine. General guidelines for the management of such reactions are provided in this section. However, severe reactions may require more intensive interventions (e.g., steroids, anti-TNF α antibodies, and/or IL-6 inhibitors).

Infusion related-reactions have occurred in a total of 37% (about 4 in 10) patients receiving treatment with MGA271. Most of the infusion-related reactions observed in patients receiving MGA271 have been mild to moderate in severity. However, six patients receiving MGA271 (< 4% of patients) have had serious or severe infusion-related reactions. These patients, some of whom were hospitalized for these reactions, recovered after receiving treatment with steroids, antihistamines, intravenous fluids, and other medications. One patient was discontinued from the study after experiencing a moderate infusion reaction.

Patients should be monitored closely for CRS symptomology in the infusion clinic for the first **2 hours after the end of the initial MGA271 infusion and then for 1 hour after the remaining infusions**. Patients should also be monitored closely for the development of other infusion-related reactions during the MGA271 infusion. Medications and supportive measures for the treatment of severe hypersensitivity reactions should be available for immediate use for an infusion reaction during study drug administration and may include, but are not limited to: subcutaneous (SC) epinephrine (0.3 to 0.5 mL of a 1:1000 solution), antihistamines (e.g., diphenhydramine 25 to 50 mg IV), corticosteroids (e.g., hydrocortisone 20-40 mg IV push or equivalent), IV fluids, vasopressors, oxygen, bronchodilators, and antipyretics. Resuscitation equipment and other supplies for the emergency management of an allergic/toxic reaction must be available. The patient should be treated according to the best available local practices and procedures. All supportive measures consistent with optimal patient care will be provided throughout the study according to institutional standards.

Should symptoms of fever or chills develop it may be difficult to distinguish among potential causes of the symptoms including emerging infection, or infusion reaction. Patients should be evaluated carefully for the presence of infection, with the acquisition of cultures and/or

implementation of empiric antibiotic therapy as appropriate based on the assessment of the Investigator. Please refer to **Section** 6.4.4 for guidance regarding the management of infusion reactions.

6.4.2 Grading of Infusion Reactions

Infusion reactions will be categorized as follows:

- Grade 1: mild reaction; infusion interruption not indicated, intervention not indicated; Note: although interruption in infusion is not indicated, temporary rate reduction indicated before resuming original rate, as patient tolerates (see **Section 6.4.4**);
- Grade 2: therapy or infusion interruption indicated but responds promptly to symptomatic treatment [e.g., antihistamines, non-steroidal anti-inflammatory drugs (NSAIDS), narcotics, IV fluids]; prophylactic medications indicated for ≤ 24 hours;
- Grade 3: prolonged (e.g., not rapidly responsive to medication and/or brief interruption of infusion); recurrence of symptoms following initial improvement; hospitalization indicated for clinical sequelae (e.g., renal impairment, pulmonary infiltrates);
- Grade 4: life-threatening consequences; pressor or ventilatory support indicated;
- Grade 5: death.

The above grading scale is the CTCAE v 4.03 grading scale for CRS, which is nearly identical to the CTCAE v 4.03 grading scale for infusion reaction and allergic reaction, and therefore considered appropriate for grading all infusion reactions in this study, irrespective of the underlying mechanism of the reaction. The Sponsor's Medical Monitor or designee should be contacted immediately if questions arise concerning the grade of the reaction.

6.4.3 Premedications and Prophylaxis

For MGA271, the following suggested guidelines (which may be modified by the investigator) are measures to be followed to avoid potential infusion reactions.

Prior to first infusion (guidelines to be followed):

- Acetaminophen 650 mg
- Diphenhydramine 50 mg or appropriate dose of equivalent H1 antagonist
- Ranitidine 300 mg or appropriate dose of equivalent H2 antagonist at the discretion of the investigator
- Hydrocortisone 20 to 40 mg (dose selected at the discretion of the Investigator)

Prior to subsequent MGA271 infusion, investigators may use the following premedications as considered indicated (suggested guidelines):

- Acetaminophen 650 mg
- Diphenhydramine 50 mg or appropriate dose of equivalent H1 antagonist
- Ranitidine 300 mg or appropriate dose of equivalent H2 antagonist
- Optional hydrocortisone 20 to 40 mg (dose selected at the discretion of the Investigator)

For subsequent MGA271 doses, patients who had infusion reactions who were not adequately or only moderately controlled with acetaminophen, diphenhydramine, or ranitidine, IV hydrocortisone at doses of 20-40 mg may be considered.

6.4.4 Management of Observed Infusion Reactions

The following are treatment guidelines for MGA271 (which may be modified as needed by the Investigator according to the best practices of medicine) for infusion reactions.

6.4.4.1 Grade 1:

- Slow the infusion rate by 50%.
- Monitor the patient for worsening of condition.
- Continue rate at 50% reduction and increase dose rate to the original rate by doubling the infusion rate after 30 minutes, as tolerated to the initial rate. Consideration can be given to beginning all subsequent infusions at 50% rate and increasing as tolerated.
- If a patient has an infusion reaction with MGA271, prophylactic preinfusion medications should be considered prior to all subsequent MGA271 infusions as written below.
- The following prophylactic preinfusion medications are recommended prior to future infusions of MGA271 for patients who experience Grade 1 infusion reactions: diphenhydramine 50 mg (or equivalent) and/or acetaminophen 650 mg at least 30 minutes before additional study drug administrations.

6.4.4.2 Grade 2:

- Stop the infusion.
- Administer diphenhydramine hydrochloride 25-50 mg IV, acetaminophen 650 mg orally for fever, and oxygen and bronchodilators for mild bronchospasm.
- Resume the infusion at 50% of the prior rate once the infusion reaction has resolved or decreased to Grade 1. The rate may then be escalated to the original rate after 30 minutes, as tolerated. Consideration can be given to beginning all subsequent infusions at 50% rate and increasing as tolerated.
- Monitor for worsening condition. If symptoms recur, discontinue the infusion; no further study drug will be administered at that visit.
- For patients with Grade 2 infusion reactions despite premedication with diphenhydramine and acetaminophen, corticosteroids (hydrocortisone 20-40 mg IV or equivalent) should be considered for acute management of the event and should be added to the premedication regimen for subsequent dosing of MGA271.

6.4.4.3 Grade 3:

- STOP THE INFUSION AND DISCONNECT THE INFUSION TUBING FROM THE PATIENT.
- TO AVOID EXACERBATION OF INFUSION REACTION OR CRS: DO NOT FLUSH THE TUBING ASPIRATE RESIDUAL DRUG FROM THE PORT LUMEN

- Administer diphenhydramine hydrochloride 25-50 mg IV, hydrocortisone 25-100 mg IV (or equivalent), and other medications/treatment as medically indicated. Higher doses of corticosteroids (i.e. methylprednisolone 2 -4 mg/kg IV) may also be considered for acute management.
- IV fluids, supplemental oxygen and bronchodilators should be considered as appropriate.
- If symptoms have resolved to baseline within 12 hours, a re-challenge may be considered at the next scheduled dose, with a 50% reduction of infusion rate. In addition, patients should be pre-medicated for this re-challenge and for any subsequent doses of MGA271 with the following: diphenhydramine hydrochloride 25-50 mg IV, oral acetaminophen 625 mg and hydrocortisone 25-100 mg IV. Patients who have a Grade 3 infusion reaction that does not resolve within 12 hours despite medical management should not receive further MGA271.
- Patients who experience a second Grade 3 infusion reaction at the time of rechallenge of MGA271 (irrespective of duration of first Grade 3 reaction), will permanently discontinue MGA271.
- Patients who experience a Grade 3 infusion reaction despite steroid premedication administration should permanently discontinue study drug.
- Report as an Immediately Reportable Event (IRE) within 24 hours.
- Report the event as a SAE, if appropriate.

6.4.4.4 Grade 4:

- Stop the infusion and disconnect the infusion tubing from the patient.
- TO AVOID EXACERBATION OF INFUSION REACTION OR CRS: DO NOT FLUSH THE TUBING.
- Administer diphenhydramine hydrochloride 50 mg IV, methylprednisolone 2-4 mg/kg IV (or more as considered appropriate), and other medications/treatment as medically indicated (e.g., an IL-6 receptor inhibitor or IL-6 inhibitor, an IL-2 receptor inhibitor, and/or an anti-TNF α antibody).
- Give epinephrine or bronchodilators as indicated.
- Support ventilation and blood pressure as indicated.
- Report as an IRE within 24 hours.
- Report the event as an SAE.
- Patients who have a Grade 4 infusion reaction will not receive further MGA271.

6.4.4.5 Grade 5:

- Report as an IRE within 24 hours.
- Report the event as an SAE.

All changes in the infusion of MGA271 including interruption of the infusion and its duration as well as reductions in infusion rate and duration must be recorded.

IRB#: IRB0010377

6.4.5 Dose Management for Adverse Events considered related to MGA271

Temporary interruptions of MGA271 may be required in the event of treatment-related toxicity. General guidelines for specific toxicity regarding dosing and treatment are provided below. All toxicities will be graded according to NCI CTCAE v4.03 (see **Section 7.1.2**).

6.4.5.1 Grade 1 or 2 AEs

Study drug administration may continue despite observation of drug-related low grade adverse events (CTCAE grade 1 or 2). If the investigator in his/her medical judgment considers that a low grade AE is of clinical significance or inordinately prolonged, the Investigator may, at his/her discretion, delay treatment to allow for resolution. Necessity to delay for more than two consecutive doses will require the patient to permanently discontinue study drug. Study drug should also be discontinued for prolonged Grade 2 AEs lasting \geq 14 days that are at least possibly related to study drug. No dose reductions are allowed.

6.4.5.2 Grade 3 or 4 AEs

Drug administration should be held upon observation of AEs of \geq Grade 3 severity to enable patient management, monitoring of the resolution of the event, and assessment of the relatedness of the event. An AE of \geq Grade 3 that is considered related to MGA271 will result in discontinuation of therapy unless otherwise specified in the protocol. For AEs associated with liver function test abnormalities, drug administration should also be discontinued for concomitant ALT >3xULN and total bilirubin >2x ULN without an alternative etiology (Hy's Law).

6.5 Concomitant Therapy

MGA271 is the only cancer drugs to be administered routinely in this study. No concomitant anticancer therapy will be given.

All concomitant medications and blood products administered during the patient's participation in the study until the post treatment follow-up visit must be recorded in the source document and on the electronic Case Report Form (eCRF). All changes in infusions, including interruptions and their duration as well as reductions in rate and duration must be recorded.

The following rules concerning concurrent treatment(s) will apply in this study:

Any other anti-neoplastic therapies including but not limited to chemotherapy or other small molecules, biologics, or radiotherapy are not allowed.

- Patients may not receive other investigational drugs during the period of study participation.
- Because MGA271 has a mechanism of action dependent upon the engagement of T lymphocytes, the use of corticosteroids should be limited to the extent possible. Chronic doses of corticosteroids in excess of 10 mg daily of prednisone or equivalent is prohibited other than for the management of drug-related adverse experiences. Steroids may be employed in the treatment of suspected MGA271-associated immune-inflammatory or autoimmune AEs in consultation with the Sponsor.
- The use of other immuno-suppressive agents is prohibited, unless they are being used to treat an adverse event.

• Use of granulocyte colony stimulating factor, granulocyte-macrophage colony stimulating factor or other growth factors is prohibited.

Patients may receive the following concurrent therapy:

- Antiemetics, antidiarrheals, anticholinergics, antispasmodics, antipyretics, antihistamines, analgesics, antibiotics and other antimicrobials, histamine receptor antagonists or proton pump inhibitors, and other medications intended to treat symptoms or signs of disease.
- Transfusions such as red blood cells and platelets are permitted to treat symptoms or signs of anemia or thrombocytopenia and should be documented on the concomitant medication form.

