5.5 Follow-Up Evaluations

Follow-up visit scheduled for 30 days and 90 days after radical prostatectomy may occur in the outpatient clinic. Required evaluations during this follow-up visits are listed below. Patients should then continue to be followed by their treating urologist according to standard institutional practices.

- performance status
- review of medication list
- review of toxicity/adverse events
- hematological laboratories and serum chemistry profile
- Serum PSA at post-operative day 90
- Sera for immunoassays
- PBMC collection for TCR Repertoire
- Whole blood for PBLs (post-op day 30 only)

Patients withdrawing from the study early because of adverse events should be followed until the adverse event has either resolved or stabilized. Reasons for premature withdrawal should be determined and documented.

In addition, patients will be required to have a structured assessment of post-operative PSA measurements for 3 years. In the first year after prostatectomy, PSA will be measured every 3 months (±1 mo). In the second and third years after prostatectomy, PSA will be measured every 6 months (±2 mo). These PSA measurements may be obtained outside of Johns Hopkins, but the results need to be made available to the study team.

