8.3.18 Time to PSA recurrence

This will be defined as the interval from the time of prostatectomy to the time when the serum PSA is ≥ 0.2 ng/mL. PSA will be measured approximately 1 month after prostatectomy, and every 3 (±1) months during the first post-operative year and every 6 (±2) months during the second and third post-operative years. For subjects who have not yet demonstrated PSA relapse at the time of censoring, patients will be censored at the date of

the last assessment that shows a lack of PSA recurrence. This outcome will be expressed as a median and will be determined using the Kaplan-Meier method.

8.3.19 In expansion cohort (Amendment 1): assessment of Gleason grade change (prostatectomy Gleason sum vs. core biopsy Gleason sum) post neoadjuvant Enoblituzumab treatment

This will be defined by comparing highest Gleason grade from pre-treatment biopsy versus highest Gleason grade from post-treatment prostatectomy. This endpoint will be expressed as the proportion of men achieving a Gleason score change.

8.3.20 Global expression profiling of pre and post treatment tumor tissue using single cell RNA sequencing, the immune NanoString immunopanel and/or microarrays

Expression profiling will be conducted as per established protocols for single cell RNA seq, Nanostring, and microarray

8.3.21 IHC analyses of CD137, CD16 and/or CD107A across potential immune infiltrate following Enoblituzumab

CD137, CD107A, and CD16 expression in prostate tumor specimens will be assessed by IHC in the prostatectomy surgical specimens (post-treatment). This endpoint will be expressed as the mean staining percentage of each of these in in tumor tissue.

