- **Regulatory T cell (T_{reg}) density**. The methods for analyzing T_{reg} infiltration will be similar to those described for CD8⁺ T cell infiltration. Descriptive statistics and graphical summaries will be provided. In addition, the CD8⁺/T_{reg} ratio and the CD4⁺/T_{reg} ratio will be computed, and reported using descriptive statistics.
- **CD4**⁺ **T cell density.** The methods for quantifying and analyzing CD4⁺ T cell infiltration will be similar to those described for CD8⁺ T cell infiltration. Descriptive statistics and graphical summaries will be provided.
- **Mean NK cell density**. The methods for quantifying and analyzing NK cell infiltration will be similar to those described for CD8+ T cell infiltration. Descriptive statistics and graphical summaries will be provided.
- **Tissue androgen concentrations**. Intraprostatic androgen concentrations (*i.e.* testosterone and dihydrotestosterone) will be summarized descriptively.
- **Enoblituzumab (MGA271) drug distribution**. Intraprostatic Enoblituzumab staining concentrations will be summarized descriptively.
- Androgen receptor (AR) quantification. Androgen receptor (AR) staining concentrations will be summarized descriptively.
- **Pathological complete responses (pCR)**. This will be defined as an absence of tumor identification on standard histological analysis of the resected prostate specimens.
- **PSA response rates**. This will be defined as an undetectable PSA (<0.1 ng/mL) at 3 months after prostatectomy. The proportion of patients achieving a PSA response will be reported. .
- **Time to PSA recurrence.** This will be defined as the interval from prostatectomy to the time when the serum PSA is ≥0.2 ng/mL. For subjects who have not yet demonstrated PSA recurrence at the time of censoring, patients will be censored at the date of the last

assessment that shows a lack of PSA recurrence. The median time to PSA recurrence after prostatectomy (*i.e.*, the median PSA-recurrence-free survival) will be estimated with 95% confidence intervals using Kaplan-Meier survival analysis.

• **Gleason grade change** post neoadjuvant Enoblituzumab treatment from pre-treatment biopsy. This will be calculated utilizing the highest Gleason grade from the pre-treatment biopsy and the post-treatment prostatectomy.

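### Time to PSA recurrence runs for 3 years with PSA ≥0.2 ng/mL as its only event, but the plan neither requires later anticancer therapy to be recorded nor takes it into account in the analysis

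*Combined protocol and SAP*

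**What the plan says.** **Event and censoring.** Section 8.3.18 defines the endpoint as "the interval from the time of prostatectomy to the time when the serum PSA is ≥ 0.2 ng/mL". Section 10.2.2 repeats this and adds: "For subjects who have not yet demonstrated PSA recurrence at the time of censoring, patients will be censored at the date of the last" (the sentence ends by naming the most recent PSA check free of recurrence). The result is a Kaplan-Meier median with a 95% confidence interval. Neither section mentions the start of other anticancer therapy.

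**Length of follow-up.** Under 5.5, "patients will be required to have a structured assessment of post-operative PSA measurements for 3 years": every 3 months in year 1, then every 6 months in years 2 and 3.

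**What is recorded, and until when.** Section 6.5 states: "All concomitant medications and blood products administered during the patient's participation in the study until the post treatment follow-up visit must be recorded". It refers to a single visit without identifying it. Section 5.5 has two: "Follow-up visit scheduled for 30 days and 90 days after radical prostatectomy may occur in the outpatient clinic". Table 1 and the list in 5.5 place medication review at these two visits and at no later point. Section 5.5 then says: "Patients should then continue to be followed by their treating urologist according to standard institutional practices". Of the PSA tests it says: "These PSA measurements may be obtained outside of Johns Hopkins, but the results need to be made available to the study team". Nothing else is required with those results.

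**Other therapy.** Section 6.5 also disallows other anti-neoplastic treatment, radiotherapy included, without saying when the restriction ends. Section 5.6 permits removal for a major violation and asks for the reason and date. Section 10.3.1 keeps eligible, dosed patients in the primary and secondary analyses despite later deviations.

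**The concern.** The endpoint depends on an untreated PSA trajectory after surgery, yet for most of the 3 years the men are in routine care, possibly elsewhere. The protocol treats PSA below 0.1 as undetectable and 0.2 as recurrence. A man whose PSA lies between the two may be given radiation or hormonal therapy. If that holds his PSA below 0.2, the stated rule credits him with recurrence-free time. If his PSA reaches 0.2 later, his event is dated late.

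Both errors lengthen the observed time, so the recurrence-free curve looks better than it would without the later therapy. The same times enter the exploratory correlation with B7-H3 expression (1.3). There is no control arm to share the error, and 2.3.1 names PSA recurrence as a possible primary endpoint for a future trial, so the estimate may be used in planning. Therapy dates not collected at the time can be hard to recover afterwards.

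**Working it through.** The documents give no expected median, event count or power for this endpoint, so there is no plan figure to reproduce. The check sets the rules side by side; the arithmetic after it is illustrative.

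**Step 1: follow one man through the rules.** Suppose his PSA is 0.15 at month 9, he starts radiation, and every later PSA to year 3 is below 0.1.

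- Event (8.3.18, 10.2.2): none, because PSA never reaches 0.2.
- Censoring (10.2.2): at his last PSA, near month 36.
- Therapy record (6.5, Table 1, 5.5): the last scheduled medication review was at day 90, so none is required at month 9.
- Data reaching the study (5.5): PSA values only.
- If the 6.5 ban applies to him: he is a deviator. Under 10.3.1 he stays in the analysis. If he is removed under 5.6, he is censored for a reason related to his recurrence risk.

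No route makes him an event.

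**Step 2: effect per man.** With all 32 men followed to year 3, the Kaplan-Meier estimate equals the simple proportion. One man moved from event to non-event changes it by 1/32 = 3.1 points.

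**Step 3: illustration of scale.** Let p be the 36-month risk of reaching 0.2 without later therapy, and f the share of would-be recurrences treated just before 0.2. Section 2.1 gives 30–50% recurrence after local therapy, with no time horizon and not specific to PSA ≥0.2 after surgery. Using it as p is an assumption. The documents give nothing for f, so 10% to 50% is assumed.

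- Treated men stay in, with PSA held below 0.2 to year 3: apparent risk = p(1 − f).
- Treated men censored at start of therapy, constant hazard: apparent risk = 1 − (1 − p)^(1 − f).

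| p | f | Stay in | Censored |
|---|---|---|---|
| 30% | 10% | 27.0% | 27.5% |
| 30% | 50% | 15.0% | 16.3% |
| 40% | 10% | 36.0% | 36.9% |
| 40% | 50% | 20.0% | 22.5% |
| 50% | 10% | 45.0% | 46.4% |
| 50% | 50% | 25.0% | 29.3% |

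**Step 4: the planned summary, the median.** With constant hazard λ = −ln(1 − p)/36, the true median is ln 2/λ: 70.0 months at p = 30%, 48.8 at 40% and 36.0 at 50%. At 30% and 40% it lies beyond 3 years with or without the problem, so the expected report is that it was not reached. At p = 50% and f = 20% it moves from 36.0 to −ln(1 − 0.5/0.8)/λ = 50.9 months if treated men stay in, or 36.0/0.8 = 45.0 months if they are censored. Both are beyond follow-up.

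**The case against.** The strongest defence is that 6.5 already bars the therapy in question. If the ban covers follow-up, treatment is a violation, 5.6 allows removal, and removal must be documented with a reason. This stands in part: for a man who is removed, the study would hold a reason. But the ban has no end date and sits beside 3 years of routine urological care, removal depends on the study learning of the therapy, and on no reading does the therapy become an event.

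A second defence is that 6.5 speaks of recording during participation, which under 5.6 lasts until follow-up is complete. So a reader might infer that the record certainly closes at day 90, but the documents do not fix that date. It is the latest scheduled medication review, and the cut-off visit itself is undefined.

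Three other stronger readings go too far:

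- That every man given later therapy is counted as recurrence-free. Only those treated before 0.2 and then held below it are affected, fully or by delay.
- That the affected men are the earliest failures. No text supports this. With PSA every 3 and later every 6 months, fast risers may pass 0.2 between tests and be counted correctly.
- That the bias has a known size. The percentages above rest on assumed p and f, and describe 3-year risk rather than the planned median.

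It is also fair that this is a secondary endpoint in a 32-man single-arm pilot, that no test or decision rule uses it, and that a PSA-only event is a coherent definition.

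**Conclusion.** The gap is real. The event and censoring rules do not take later anticancer therapy into account, and the required data after the follow-up visits would not reveal it. Neither the 6.5 ban nor the analysis population in 10.3.1 closes the gap. Assuming later therapy lowers PSA, any error lengthens observed times, so the bias in the Kaplan-Meier curve favours the drug; the same lengthened times enter the B7-H3 correlation.

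The size cannot be derived from the documents. It is 3.1 points of 3-year recurrence-free proportion per affected man with complete follow-up, and the number of such men is unknown. In the illustration the 3-year risk is understated by 3 to 25 points if treated men stay in, and by about 2.5 to 21 if they are censored. These figures show scale and are not estimates. The planned median may not change at all if it is not reached within 3 years, as at 30% or 40% recurrence. This is a low-cost improvement to a secondary endpoint, not a flaw that undermines the trial.

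**What to change.** 1. In 6.5 and Table 1, require the type and start date of any post-operative anticancer therapy with each PSA report through year 3, and state which visit ends the general medication record.
2. Reconcile the undated ban in 6.5 with the 3 years of follow-up under standard practice in 5.5. Which reading applies is for the sponsor and investigators to decide.
3. In 8.3.18 and 10.2.2, keep the PSA-only definition. Add a pre-specified analysis in which the event is the earlier of PSA ≥0.2 ng/mL and the start of such therapy. Report therapy started at undetectable PSA (<0.1 ng/mL) separately.

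The added analysis should sit beside the PSA-only one and not replace it: a composite would count adjuvant therapy at undetectable PSA as recurrence, which errs in the opposite direction. Shown together, the two indicate how far the result depends on later therapy.

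The cost is one extra case report form item per PSA report already required, and one extra analysis. The item should be collected prospectively.
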